## 2. STUDY BACKGROUND AND RATIONALE

**2.1 CLINICAL RELEVANCE OF SVA.** SVA is the most common cause of fetal tachycardia  $\geq 180$  bpm, affecting 1/4,000 pregnancies. Despite its relative rarity, it is a *leading cause of fetal heart failure, prematurity and perinatal death*. The development of fetal hydrops (defined by >1 of these symptoms: abdominal, pleural, pericardial effusion(s); skin edema) is associated with *perinatal mortality as high as 35%*. The risk of hydrops increases if SVA presents at a younger gestational age and is rapid and enduring, but even intermittent SVA may

have serious consequences. In the largest retrospective study to date on fetal SVA by [name] et al, 40% of 114 fetuses with SVT presented with hydrops, which was associated with a perinatal mortality rate of 21%. In another study by Simpson et al, fetal hydrops occurred in 41% of 127 SVA cases and was associated with 27% mortality. In the absence of fetal hydrops, the risk of SVA-related perinatal mortality is much lower (0%-4%).

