## 2.5 EFFICACY OF TRANSPLACENTAL THERAPY.

[figure not shown]
**PROSPECTIVE STUDY.** There are no other prospective randomized studies of fetal SVA therapy to date.

**RETROSPECTIVE STUDIES.** Retrospective studies report inconsistent success rates for all 1st line agents in treating fetal SVA. In studies (total n=226) using oral **digoxin** monotherapy, in-utero cardioversion has been reported in 50% to 100% of SVA *without* hydrops, but in <20% of SVA *with* hydrops. **Flecainide** (n=70) has resulted in sinus rhythm in 58% to 100% of SVA cases *without* hydrops and in 43% to 58% of those *with* hydrops. **Sotalol** (n=56) has been successful in 40% to 100% of SVA *without* hydrops, and in 50% *with* hydrops. While the studies confirm that there is no single medication that can convert all fetal SVAs to a normal rhythm, direct comparisons of study results is impossible as study cohorts varied in disease severities, definitions of treatment success, drug doses, schedules, and many other factors. Data on the impact of the same agents as 2nd line monotherapy or in combination to treat therapy-resistant SVA is largely unavailable.

**DRUG COMPARISONS.** The only study to directly compare transplacental drug therapies by [name] et al., an initiator of the FAST Therapy Trial, represented the experience of 3 sites, each using a different 1st line agent. An adverse primary outcome, defined as a) preterm delivery, b) perinatal death, or c) persistent SVA to birth, was documented in 45% of 75 treated SVT cases (outcome a) 32%; b) 8%; c) 5%) and 58% of 36 treated AF cases (a) 50%; b) 3%; c) 6%), and was mainly related to *incomplete SVA control at the time of the event*. However, [name]'s study also demonstrated that the fetal response to treatment independently depended on the *SVA pattern, fetal state* and the *choice of 1st line therapy*. AF [Fig. 1] and fetal hydrops [Fig. 2] were independently associated with

[figure not shown]

**Fig. 1. Freedom from termination of fetal SVT vs. AF despite drug treatment (n=111).** AF responded more slowly to drug therapy than SVT (HR=2; p=0.005). Cardioversion at 5 and 10 days was achieved in 50% and 63% of fetuses with SVT and in 25% and 41% of cases with AF.

[figure not shown]

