**2.6 SAFETY OF TRANSPLACENTAL THERAPY** There is extensive retrospective data on the safe use of digoxin, sotalol, and flecainide, either alone or when used in combinations for this indication, with the limitation that AEs were most likely inconsistently documented and thus underreported in retrospective studies. Although minor drug-related AEs are not infrequent patient complaints based on our own retrospective experience and drug monographs, life-threatening AEs owing to the use of fetal antiarrhythmic drug therapy in predominantly healthy mothers have not been reported. However, virtually all antiarrhythmic agents may have the potential to provoke new or to exacerbate existing arrhythmias. This risk increases with toxic drug levels, maternal heart disease, ventricular arrhythmia, and hypokalemia. Previously reported mortality rates of treated fetuses with SVA *without* hydrops were between 0% and 5%, whereas about 20% of fetuses with SVA *with* hydrops had died, usually due to treatment-resistant SVA. In our large experience, we never observed unexpected SAEs, irrespective whether single or multiple drug therapy was used.

*To minimize risks of SAEs* a) only mothers without serious health and pregnancy concerns other than fetal SVA are eligible for participation in the RCTs (**see Section 7.2**); b) the primary physician and participant both are informed about the assigned drug therapy from the time of randomization to study end (open label trial); c) drug dosages will be used that are considered to be safe and effective (**see 7.6**), thus avoiding toxic levels (digoxin) and excessive QTc prolongation >0.5 (sotalol); and d) initiation of therapy is recommended in-hospital to monitor maternal/fetal heart rates and wellbeing, followed by serial outpatient encounter once arrhythmia control is achieved (**see 7.7**).

[figure not shown]

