#### **SECONDARY OUTCOME**

- Proportion of participants with cardioversion over time
- Proportion of participants with treatment failure
  - Number of participants with treatment failure compared to number of participants with successful treatment.
  - Treatment failure is defined as one of the following:
    1. cross-over to another drug
    2. SVT/AF that persists to birth
    3. preterm birth
    4. death
- Cause of death (prenatal, postnatal)
- Proportion of participants with arrhythmia related death
- Average gestational age at birth
- Birth weight (z-scores)
- Average days of maternal and neonatal hospitalization related to SVA therapy
- Maternal prevalence of pregnancy/treatment-related AEs and outcomes
- Proportion of AEs / adverse outcomes (prenatal, postnatal)

The primary outcome measure is absolute (term delivery without tachyarrhythmia) with no room for interpretation. Secondary outcomes will be the time interval from treatment initiation to the beginning of permanent cardioversion, and once established, the freedom from SVA recurrence on maintenance therapy. Only the final outcome will be considered to classify cases. Cross-over to another agent, fetal demise, development of fetal hydrops, and delivery for SVA will be considered treatment failures. Any recurrence of fetal SVA after

documentation of a normal cardiac rhythm >24 hours by echocardiography will be classified as maintenance treatment failure.

**7.11 STATISTICAL ANALYSES.** All statistical analyses using SAS (SAS Institute, Cary NC) with standard settings will be performed by very experienced statistician from the Cardiovascular Data Management Centre (CVDMC) at SickKids. As a general precept, all 3 RCTs will be analyzed separately. RCT analyses will be performed on an *intention-to-treat basis*, although a separate subgroup analysis will be performed. Descriptive statistics for all study variables, for each study groups separately, will be created using means with standard deviation, median with inter-quartile range, and frequencies as appropriate. Baseline characteristics that should be equally distributed between groups through randomization (age at diagnosis, baseline fetal heart rate, incessant vs. intermittent SVA, maternal age) will be assessed in a test of randomization. The test of randomization will be performed using Fisher’s exact test for categorical variables and Student’s t-test (with Satterthwaite method for variance estimation) for continuous variables.

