The **PRIMARY OUTCOME** (proportion of term deliveries without SVA) will be a binary outcome (yes/no). For this type of outcome, the proportion of participants in each therapy arm will be compared using logistic regression models (PROC LOGISTIC) with likelihood ratio test to determine regression model fit, Wald chi-square test from maximum likelihood estimates (Fisher’s scoring technique) to determine statistical significance of the therapy arm and c-statistic from the regression model’s area under the curve (AUC) to measure model accuracy. Effect size estimate and standard error will be converted into odds ratio with 95% confidence (95% CI) limits to facilitate comparisons between the different trials.

**SECONDARY OUTCOME** will also be expressed as binary variables (incl. proportions of participants: requiring 2nd line therapy and 3rd line therapy; with SVA recurrence on maintenance therapy; delivery without SVA termination; death <1 month; etc.) will be assessed between the different therapy arms in the same way as the primary outcome. For outcomes with time dependent variables (proportion of participants with cardioversion over time; timing of mortality from initiation of therapy), Kaplan-Meier survival curves will be used to depict the event proportion over time for each group. Single phase parametric hazard regression model (PROC PHREG) will be used to compare the 2 therapy arms (with likelihood ratio test to determine regression model fit and maximum likelihood estimates chi-square to determine statistical significance of the therapy arm. Effect size estimate and standard error will be converted into hazard ratio with 95% CI to facilitate comparisons between the different trials. Finally, for outcomes with continuous variables (average gestational age at birth/birth weight z-score; average days of neonatal hospitalization related to SVA therapy), linear regression models using maximum likelihood estimates for parameter estimation will be used (PROC GENMOD: Akaike's information criterion (AIC) criterion to assess regression model fit; Wald chi-square test from maximum likelihood estimates). Effect size estimate and standard error will determine the difference between the therapy arms in the same original units of measurement as the outcome.

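### The planned Wald test for death breaks down if exactly one arm has no deaths, which is a realistic result in RCT A and RCT B

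*Combined protocol and SAP*

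**What the plan says.** Section 7.11 of the combined protocol and SAP analyses the primary outcome with PROC LOGISTIC. The Wald chi-square from maximum likelihood decides significance of the therapy arm. The odds ratio and its 95% interval come from the estimate and standard error. The likelihood ratio test is assigned to model fit only.

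Binary secondary outcomes "will be assessed between the different therapy arms in the same way as the primary outcome", and the list includes "delivery without SVA termination; death <1 month; etc". Section 7.10 also lists "Proportion of participants with arrhythmia related death" as a secondary outcome.

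Timing of mortality is to be compared in PROC PHREG, with "maximum likelihood estimates chi-square to determine statistical significance of the therapy arm" and a hazard ratio and interval again built from the estimate and standard error.

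The opening of Section 7.11 fixes the software choice: "All statistical analyses using SAS (SAS Institute, Cary NC) with standard settings". Fisher's exact test appears once, for the baseline test of randomization. No penalised or exact method is named for any outcome.

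**The concern.** A Wald test needs a finite estimate and a meaningful standard error. When one arm has no events, the maximum-likelihood log odds ratio (or log hazard ratio) is infinite and its standard error grows faster than the estimate. Their ratio therefore tends to 0 and the p-value to 1. The printed result then depends on where the software stops iterating and not on how many deaths the other arm had.

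The plan's own background makes such counts plausible without hydrops. Section 2.1 puts SVA-related perinatal mortality there at 0% to 4%. Section 2.6, on treated fetuses, says rates without "hydrops were between 0% and 5%, whereas about 20% of fetuses with SVA" with hydrops. Section 2.5 reports 3% perinatal deaths among 36 treated AF cases, hydrops status not given.

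Two things are at stake. The planned between-arm result for death could not be reported, and a p-value near 1 beside a lopsided death count could be misread as reassurance. A replacement method would also have to be chosen after the deaths were known, and that choice can decide significance: at 0 versus 5 deaths Firth gives 0.025 and Fisher 0.059.

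**Working it through.** **Inputs.** Section 3.2 gives 93 per arm (RCT A), 89 (RCT B) and 93 (RCT C), two-sided 0.05, 80% power, and +20 percentage points from 30%, 55% and 30%. The pooled-variance two-proportion formula without continuity correction reproduces 93, 89 and 93, with power 80.0%, 80.4% and 80.0%. The arm sizes are therefore taken as stated. Mortality rates of 1% to 5% are assumptions within the documents' 0%-5% range. At 5%, expected deaths are 0.05 × 93 = 4.7 per arm.

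**The planned test at 0/93 versus 6/93.** Iterating the maximum-likelihood fit and stopping at three points:

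| Iterations | Logistic log OR (SE) | Wald p | Cox log HR (SE) | Wald p |
|---|---|---|---|---|
| 8 | -6.5 (10.3) | 0.53 | -9.2 (40.7) | 0.82 |
| 12 | -10.5 (76.3) | 0.89 | -13.2 (301) | 0.97 |
| 20 | -18.5 (4168) | 0.997 | -21.2 (16,400) | 0.999 |

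Neither fit converges. With 0 versus 8 deaths the logistic p is still 0.996 at 20 iterations, where Fisher's exact test gives 0.007.

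**Other tests on the same kind of table** (89 or 93 per arm agree within rounding):

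| Deaths | Wald (limit) | Likelihood ratio | Fisher | Firth, penalised LR |
|---|---|---|---|---|
| 0 vs 3 | 1 | 0.040 | 0.246 | 0.108 |
| 0 vs 4 | 1 | 0.018 | 0.121 | 0.052 |
| 0 vs 5 | 1 | 0.008 | 0.059 | 0.025 |
| 0 vs 6 | 1 | 0.0035 | 0.029 | 0.012 |

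For a 2×2 table the Firth estimate amounts to adding one half to each cell. For 0/89 versus 6/89, OR = (6.5/83.5) / (0.5/89.5) = 13.9, with profile interval 1.6 to 1828.

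**How often exactly one arm has no deaths.** With equal mortality p, let z = (1-p)^n. Then P(exactly one arm at zero) = 2z(1-z), and P(0 versus 5 or more) = 2z × P(X ≥ 5), with X binomial(n, p). Example: p = 1%, n = 93 gives z = 0.393 and 2 × 0.393 × 0.607 = 0.477.

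| Mortality, both arms | Exactly one arm at zero | Neither arm has a death | 0 vs 5 or more |
|---|---|---|---|
| 1% | 48% | 15-17% | 0.2% |
| 2% | 26-28% | 2-3% | 1.1-1.2% |
| 3% | 11-12% | 0.4% or less | 1.7% |
| 4% | 4-5% | 0.1% | 1.4-1.5% |
| 5% | 2% | below 0.1% | 0.9-1.0% |

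The chance that at least one of RCT A and RCT B is affected, at 2%, is 1 - (1 - 0.259)(1 - 0.276) = 46%. At 3% it is 22%.

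If true rates differ, each arm has its own z. At 1% versus 4%, exactly one arm is at zero in 40-41% of trials and the count is 0 versus 5 or more in about 12%. At 0% versus 5% these become 99% and 46-50%.

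**Power and type I error**, by full enumeration of both binomial counts, with Wald not rejecting when an arm is at zero:

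- Power at 1% versus 4%: Wald 1%, Firth 14-16%. At 0% versus 5%: Wald 0%, Firth 46-50%.
- Type I error of the ordinary likelihood ratio test: 7-9% at 2% to 5% mortality.
- Type I error of Firth: 0.2% at 1%, 1.2-1.4% at 2%, 2.5-2.6% at 3%, 3.8-3.9% at 5%.

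**RCT C.** At 20% mortality in both arms, z = 0.8^93 = 9.7 × 10⁻¹⁰, so the chance of exactly one arm at zero is about 2 in 1 billion.

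**The case against.** The case against acting has five parts.

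- **Small effect on decisions.** At equal mortality the significance call changes in at most about 1.7% of trials. The large figures need contrasts such as 0% versus 5%, which no document proposes. The trial is sized on the primary outcome only. This stands and limits the weight of the point.
- **Deaths stay visible.** Frequencies by arm and Kaplan-Meier curves would show them, death counts against the primary outcome, and a runaway odds ratio beside a zero count is hard to miss. This also stands, but Section 7.11 still plans a between-arm test of death, and that test would have no usable result.
- **The mortality range may not match.** The 0%-4% in Section 2.1 is SVA-related, while death before one month is not limited by cause and could be more frequent. Above about 1%, that makes a zero-death arm less likely. The opposite holds if the outcome excludes fetal death. Both are uncertainties in the rate; the failure itself does not depend on them.
- **Other remedies exist.** Fisher's exact test is already in the plan and would also give a valid p-value. It gives no odds ratio or interval in the form the plan reports, and Firth's interval, though finite, is very wide.
- **The hazard model is described loosely.** The plan calls it parametric but names PROC PHREG, and does not use the word Wald there. A chi-square on maximum-likelihood estimates is most naturally the Wald test, and the hazard ratio diverges under either reading. The Firth correction proposed here does assume that PROC PHREG is meant.

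**Conclusion.** The concern holds and the plan should be changed. It is a stated rule that fails under plausible counts. With no deaths in exactly one arm, the planned odds or hazard ratio, interval and p-value are unusable for death before one month, arrhythmia-related death and timing of mortality.

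In RCT A and RCT B this is likely at about 1% to 2% mortality, less likely at 3%, and uncommon at 4% to 5% unless the arms differ. In most affected trials the loss is a reportable estimate and interval. Among results with one arm at zero, the significance call against Firth changes only at 0 versus 5 or more deaths.

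The primary outcome and the sample size are untouched, and RCT C is safe in practice if both arms are near 20%.

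The sizes assume true rates within the documents' range, fetal deaths included in death before one month, and, for the Cox figures, deaths at distinct times with everyone else followed to the end.

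**What to change.** Amend the secondary-outcome text of Section 7.11 as follows.

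- For death before one month and arrhythmia-related death, name Firth-penalised logistic regression with the penalised likelihood ratio test and profile-likelihood 95% interval, whatever the observed counts. At 0/93 versus 5/93 this gives OR 11.6 (1.3 to 1534), p = 0.025.
- For timing of mortality, use the Firth correction in PROC PHREG with the matching test and interval. At 0 versus 6 deaths with 89 per arm this gives HR 13.4 (1.6 to 1745), p = 0.012. Confirm at the same time that the PROC PHREG model is the one intended.
- If neither arm has a death, report counts only.
- Do not promote the ordinary likelihood ratio test to this role, given its 7-9% type I error here.

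The test and interval must change along with the estimator. At 0/89 versus 6/89 the Firth estimate with an ordinary Wald test gives log OR 2.63 / SE 1.48 = 1.79, p about 0.07, against 0.012 by the penalised likelihood ratio test.

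The cost is two sentences in the SAP and a few lines of SAS, with no change to data, sample size or other outcomes. The drawbacks are a conservative test at very low mortality and very wide upper limits when an arm has no deaths. Applying the same rule in RCT C changes almost nothing: 12/93 versus 25/93 gives Wald OR 2.48 (1.16 to 5.31), p = 0.019, and Firth OR 2.43 (1.17 to 5.28), p = 0.017.

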**Fig. 2. Freedom from termination of fetal SVT with and without hydrops (n=75).** Treatment failure was also more likely if SVT was associated with fetal hydrops (HR=1.8; p=0.04) at the time of diagnosis. It took more than twice as long (9 vs. 4 days) for conversion of 50% of SVT cases to a normal rhythm if fetuses were hydropic. 21% of the hydropic cases died.

[figure not shown]
lower cardioversion rates. On the other hand, 1st line monotherapy with sotalol resulted in faster/higher AF termination rates [Fig. 3] while flecainide or digoxin was superior in terminating SVT [Fig. 4] and in lowering tachycardia rates if SVA persisted [Fig. 5]. None of the agents as 2nd line therapy was associated with a greater rate of SVA termination although **sotalol** tended to be superior for AF. Once fetal SVA was converted to sinus rhythm, chronic drug therapy to birth with the drug(s) that successfully terminated the SVA was used to prevent recurrences. Recurrence of SVT and AF was documented in 8% and 15% of cases during the first month of maintenance treatment.

**Fig. 3. Freedom from termination of fetal AF (n=36):** For patients with AF, in multivariate models adjusted for arrhythmia pattern, 1st line sotalol was associated with a greater likelihood of AF termination compared with digoxin (HR: 5.4; p=0.05) or flecainide (HR: 7.4; p=0.03). Time to conversion of 50% was 12 days with sotalol, but not achieved with the other drugs before delivery.

**Fig. 4. Freedom from termination of fetal SVT (n=75):** For patients with SVT, in multivariate models adjusted for hydrops and SVT pattern, the use of flecainide (HR: 2.9; p=0.01) or digoxin (HR: 2.1; p=0.02) as 1st therapy were associated with increased likelihood of SVT termination compared to sotalol. The median time to conversion of 50% of cases was 3 days with digoxin, 4 days with flecainide but 12 days with sotalol.

**Fig. 5. Effects of 1st line treatment on tachycardia rates.** When incessant SVT (n=23) or AF (n=22) persisted to day 5 of treatment, ventricular rates were lowered more with flecainide and digoxin than with sotalol (p<0.001). This suggests that flecainide and digoxin are similarly effective in reducing the tachycardia to better tolerated rates while sotalol has no or only modest heart rate slowing effects.

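### The Kaplan-Meier cardioversion curve has no rule for fetuses delivered or dying before conversion; if they are censored, it overstates the proportion converted

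*Combined protocol and SAP*

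**What the plan says.** Section 7.10 lists the proportion of participants with cardioversion over time as a secondary outcome, and later describes it as the "time interval from treatment initiation to the beginning of permanent cardioversion". Section 7.11 displays it by Kaplan-Meier: "Kaplan-Meier survival curves will be used to depict the event proportion over time for each group". For the arm comparison it states: "Single phase parametric hazard regression model (PROC PHREG) will be used to compare the 2 therapy arms". The subgroup paragraph of 7.11 reuses cardioversion over time to compare SVT and AF with and without hydrops.

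No section gives a censoring rule, a competing-event rule or an end of follow-up for this curve. The nearest text defines other endpoints. Sections 7.7 and 7.10 count fetal demise, preterm birth, SVA lasting to birth and delivery for SVA as treatment failure, and 7.10 adds that cases are classified by final outcome only. Section 7.11 also lists "delivery without SVA termination" and death before 1 month as binary outcomes. None of this says when, or with what status, an unconverted fetus leaves the cardioversion curve.

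**The concern.** Delivery or death ends the chance of conversion in utero. Censoring such a fetus treats it as though it could still convert at the same rate as those still under treatment. One minus Kaplan-Meier then estimates conversion in a hypothetical setting where nobody is delivered or dies unconverted, while the axis will be read as the proportion of participants converted.

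The documents show that these exits are expected and tied to non-conversion. Section 2.3 attributes the 37% preterm delivery among treated cases to failure to control the arrhythmia rapidly. Section 2.5 links adverse outcomes mainly to incomplete control at the time of the event. It also reports that 50% conversion of AF was not reached before delivery with digoxin or flecainide, and that "21% of the hydropic cases died". Under section 7.7 the physician may deliver at any time on clinical judgement, and the trial is open-label, so exit rates could differ by arm. At stake is whether the curves show the proportions actually converted, both between arms and across the SVT, AF and hydrops groups.

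**Working it through.** **Plan's own figure.** The plan states no figure for this curve. Its only related calculation, the primary-outcome sample size in section 3.2, reproduces with the pooled-variance formula for two proportions (two-sided 0.05, power 80%): 30% vs 50% gives 93 per arm and 55% vs 75% gives 89 per arm, so 2 × (93 + 89 + 93) = 550.

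**Formulas.** Let hc be the conversion hazard, hd the hazard of unconverted exit, and Hc and Hd their cumulative values.
- Exits censored: 1 − KM(t) = 1 − exp(−Hc(t)).
- Actually converted: CIF(t) = ∫ hc(u)·exp(−Hc(u) − Hd(u)) du.
- Excess = (1 − KM) − CIF, taken at day 28 (an assumed reading point).

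**Conversion hazards per day, from section 2.5.**
- AF: 41% converted at 10 days, so hc = −ln(0.59)/10 = 0.0528.
- SVT without hydrops: "Cardioversion at 5 and 10 days was achieved in 50% and 63% of fetuses with SVT", so hc = ln 2/5 = 0.139 to day 5, then ln(0.50/0.37)/5 = 0.060, assumed to hold to day 28. That cohort mixes hydropic and non-hydropic SVT.
- SVT with hydrops: median 9 days, so hc = ln 2/9 = 0.0770, assumed constant.

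**Eventual unconverted-exit shares s (assumptions).**
- Low case: 5% in every group.
- AF high case: 3% death + 6% persistent SVA = 9% (2.5).
- SVT without hydrops high case: 4% death (top of the range in 2.1) + 5% persistent SVA (2.5) = 9%.
- SVT with hydrops: 10% as a middle value and 21% (2.5) as an upper case.

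**Worked case, hydrops, s = 21%, exits from day 0.** hd = 0.0770 × 0.21/0.79 = 0.0205. 1 − KM = 1 − exp(−0.0770 × 28) = 88.4%. CIF = 0.79 × (1 − exp(−0.0975 × 28)) = 73.8%. Excess 14.6 points.

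For each group and share there are three timings: exits from day 0; exits from day 14 with hd raised so that the eventual share is still s; and exits from day 14 with the day-0 hd, which lowers the eventual share. The cases without a closed form were integrated numerically.

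| Group | 1 − KM, day 28 | s | CIF, exits from day 0 (excess) | CIF, from day 14, same s (excess) | From day 14, same hd: eventual share; excess |
|---|---|---|---|---|---|
| AF | 77.2% | 5% | 74.9% (2.2) | 76.3% (0.9) | 2.4%; 0.4 |
| AF | 77.2% | 9% | 73.1% (4.1) | 75.4% (1.8) | 4.3%; 0.8 |
| SVT, no hydrops | 87.5% | 5% | 84.7% (2.8) | 86.3% (1.2) | 2.0%; 0.4 |
| SVT, no hydrops | 87.5% | 9% | 82.4% (5.1) | 85.1% (2.4) | 3.6%; 0.8 |
| SVT, hydrops | 88.4% | 5% | 85.2% (3.2) | 86.8% (1.6) | 1.7%; 0.5 |
| SVT, hydrops | 88.4% | 10% | 81.8% (6.6) | 84.8% (3.6) | 3.4%; 1.1 |
| SVT, hydrops | 88.4% | 21% | 73.8% (14.6) | 78.2% (10.2) | 7.1%; 2.4 |

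**Two arms, hydrops, same conversion hazard, s = 5% vs 21%.** Both censored curves read 88% at day 28. Actually converted: 85% vs 74% with exits from day 0, or 87% vs 78% with exits from day 14 and the same shares.

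**Direction.** In 2,000 simulated arms of 93 for each of three scenarios (hydrops s = 21%; AF s = 30% and 9%; exits from day 0), 1 − KM was never below the cumulative incidence. The two agree only if no conversion follows an unconverted exit.

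**Scale.** One standard error of an arm's proportion at 93 per arm is √(0.88 × 0.12/93) = 3.4 points, or √(0.74 × 0.26/93) = 4.5 points.

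**The case against.** **The plan never says that exits are censored.** This stands. The text "All statistical analyses using SAS (SAS Institute, Cary NC) with standard settings" does not settle it, because the analyst codes the event status and the software has no default for a delivery. A reader might infer from that phrase that the plan commits to a biased curve; the documents do not support this. The final-outcome sentence in 7.10 could even be read as keeping such fetuses in the risk set as never converted, which would make the curve correct. The wording is ambiguous, so the bias is conditional on censoring.

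**The hazard ratio is not wrong.** Largely stands. If exits are censored, PROC PHREG gives a valid cause-specific hazard ratio. If they are kept at risk, the same run estimates a subdistribution-type ratio. So the missing rule leaves the meaning of the hazard ratio open, but does not make it invalid.

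**The numbers are soft.** Stands. Day 28, the shares and the timing are assumed. The 21% is perinatal mortality, so it may include neonatal deaths or deaths after conversion, and section 2.5 cites a series with no mortality under digoxin plus flecainide in hydropic SVT. The AF value of 77% at day 28 is high for digoxin, given that 50% was not reached before delivery. For non-hydropic SVT, the 4-day median in Fig. 2 would instead give 99.2% vs 94.4% at s = 5% with exits from day 0. Several of the results lie within one standard error.

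**Other outcomes already show the failures.** Partly stands. The binary outcomes reveal part of any difference in exits, but they do not correct the curve.

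**Conclusion.** The concern holds as a conditional one: the rule is missing, and the usual practice of censoring would overstate the proportion converted. With 5-21% eventually exiting unconverted, the day-28 excess is about 2-15 points for exits from day 0 and about 1-10 points for exits from day 14 with the same shares. It falls to 0.4-2.4 points if only about 2-7% exit, from day 14 on. These are illustrations, not estimates for this trial. The excess would be larger if many of the preterm births in section 2.5 (50% of AF, 32% of SVT) came before conversion, but the documents do not give that share.

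A reader might infer that the trial's main conclusions are at risk. They are not: the primary outcome is binary and analysed by logistic regression, and the sample size and interim rule do not use this curve. The point should be fixed because the outcome is a listed secondary one and the remedy is cheap.

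**What to change.** In section 7.11, for the cardioversion outcome and for the subgroup comparison of cardioversion over time:
- Replace the Kaplan-Meier display with cumulative incidence (Aalen-Johansen) by arm.
- Treat delivery or death before the section 7.10 cardioversion endpoint as a competing event, and censor only withdrawal or loss to follow-up. Keeping such fetuses at risk as never converted to a fixed horizon is an acceptable equivalent for the curve.
- Follow participants through cross-over under intention-to-treat, and state that the curve shows conversion on any line of therapy.
- Classify deliveries in sinus rhythm by the plan's own conversion definition (7.7 and 7.10).
- For PROC PHREG, censor these exits and label the result a cause-specific Cox hazard ratio. The procedure fits a Cox model, so the single-phase parametric description should go.

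The cost is SAP wording and a few lines of SAS. Section 7.8 already captures the dates of cardioversion, birth and demise. The downside is slightly lower stated conversion proportions.
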